4. ANALYSIS AND REPORTING

4.1 Interim Analysis

No formal interim analysis is planned for this study, but the study will be monitored by a Data Safety Monitoring Board (DSMB), which will advise the Sponsor regarding the continuing safety of study subjects and potential subjects as well as the continuing validity and scientific merit of the trial.

4.2 Final Analysis

All final, planned analysis identified in the protocol and in this SAP will be performed after the last subject has completed the Follow-up Safety Visit and all relevant study data have been processed and integrated into the analysis data base.

Any post-hoc, exploratory analysis completed to support planned study analysis, which were not identified in this SAP, will be documented and reported in appendices to the CSR. Any results from these unplanned analyses (post-hoc) will also be clearly identified in the text of the CSR.

5. ANALYSIS POPULATIONS

The following analysis populations are planned for this study:

- **Safety Population (SAFETY):** The Safety Population includes all subjects who receive at least one dose of open-label study drug after the Baseline Visit for HZNP-ACT-302. All analyses will be based on the Safety Population unless otherwise noted.

5.1 Sample Size

Subjects who complete 26 weeks of blinded treatment in Study HZNP-ACT-301 will be eligible for enrollment. The sample size is not based on statistical considerations; therefore no inference will be drawn from any statistical tests conducted.

6. GENERAL ISSUES FOR STATISTICAL ANALYSIS

Data processing, tabulation of descriptive statistics, calculation of inferential statistics, and graphical representations will be performed using SAS® Software (release 9.3 or higher) for Windows, unless otherwise specified.

Continuous (quantitative) variables will be summarized using descriptive statistics including number of non-missing values, mean, standard deviation (SD), median, minimum, and maximum.

Categorical (qualitative) variables will be summarized using the number and proportion of each possible value. In general, the denominator for the percentage calculation will be based upon the total number of subjects in the study population for the treatment group.

The minimum and maximum will be reported with the same degree of precision (i.e., the same number of decimal places) as the raw data. Measures of location (mean and median) will be reported to 1 degree of precision more than the raw data and measures of spread (standard deviation) will be reported to two degrees of precision more than the raw data.

Assessments done on unscheduled visits will not be summarized but will be listed. All analyses will be completed on the Safety Population unless otherwise specified. Additionally, all summaries will be presented by overall treatment.

All final, planned analyses identified in the protocol and in this SAP will be performed after all relevant study data have been processed and integrated into the analysis database, analysis populations have been finalized, and the database has been locked. Any post-hoc, exploratory analysis completed to support planned study analyses, which were not identified in this SAP, will be documented and reported in Section 9.8 of the CSR. Any results from these unplanned analyses (post-hoc) will also be clearly identified as subject in the text of the CSR.

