9.4.1.1 Dose Adjustment Guidelines

The dose of ACTIMMUNE is based on the subject's BSA; therefore, height and weight will be measured at Baseline/Day 1 (Week 26 of Study HZNP-ACT-301) and Weeks 4 and 13, and the dosing volume will be determined using the formula presented in [Section 9.4.7.2](#).

The planned 4-week dose escalation schedule will be implemented if it is tolerated by the subject. If, however, in the opinion of the investigator, the subject experiences severe reactions during dose escalation, the dose will be reduced to the previous dose level, or will be interrupted until the adverse reaction resolves and then restarted at the previous or a lower dose level. Once the previous/lower dose level is tolerated, the dose may then be titrated upwards again to the next dose level as tolerated.

During the dose-escalation period, the clinical site will contact the subjects (or caregivers/legal representatives) via phone calls or email on a weekly basis to monitor AEs and dosing logistics. In addition, subjects may contact the clinical site at any time with dosing or possible drug reaction concerns throughout the study. Dose adjustments may be continued through Week 13, but at Week 13, all subjects should be on a stable tolerated dose and remain at that dose through Week 26. During the stable dosing period, subjects will be contacted by the site via phone calls or emails on a monthly basis to monitor AEs and dosing logistics. Although the dose may not be further increased after Week 13, it may be reduced on a case-by-case basis to manage subsequent drug-related AEs (e.g., elevated liver function tests).

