6.1 Visit Windows

Subjects who withdraw from the study will have their data collected at the premature withdrawal (PW) visit assigned to the closest scheduled visit (either prior or post PW) where the data was scheduled to have been collected based on the protocol schedule of events. The data collected closest in time and date to protocol scheduled timing will be used for analysis.

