6.2 Data Adjustments, Handling, Conventions

All collected data will be presented in listings. Data not subject to analyses according to this plan will not appear in any tables or graphics but will be included only in the data listings.

Adverse events will be coded using the Medical Dictionary for Regulatory Activities (MedDRA) (version 16.1). Concomitant medications will be coded using World Health Organization Drug Dictionary (WHO-DD) (version March 1, 2013).

If partial dates occur, the convention for replacing missing dates for the purposes of calculating derived variables is as follows:

If an AE has a missing severity, it will be imputed as 'Severe'; any missing relationship to study drug of an AE will be imputed as 'Related'. No other missing data will be imputed unless otherwise specified.

In general, for quantitative laboratory values reported as '<' or ' \leq ', the lower limit of quantitation (LLOQ), or limit of detection (LOD), the reported value (i.e., LLOQ, LOD) will be used for analysis).

For quantitative laboratory values reported as '>' or ' \geq ', the upper limit of quantitation (ULOQ), the reported value (i.e., ULOQ) will be used for analysis.

For analysis purposes, repeat laboratory test results will not be used unless the original laboratory value is missing or indicated as invalid, in which case the first non-missing repeat laboratory value will be used for data analysis.

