6.3 Derived and Computed Variables

The following derived and computed variables have been initially identified as important for the analyses of Safety, Efficacy and Exploratory endpoints. It is expected that additional variables may be required. The SAP will not be amended for additional variables that are not related to the primary target or key secondary target variables. Any additional derived or computed variables will be identified and documented in the SAS programs that create the analysis files. If the SAP is not amended, further derivations related to primary and secondary target variables will be described in the CSR.

- 302 Baseline = The last non-missing measurement/assessment on the date of Week 26 Visit from HZNP-ACT-301. If this measurement is missing or otherwise unavailable, it will be the last non-missing measurement/assessment on or prior to first dose in HZNP-

ACT-302.

- 301 Baseline = The last non-missing measurement/assessment prior to first dose of Study in HZNP-ACT-301.
- Study Day = Assessment Date – Date of Enrollment + 1
- Change from Baseline = Value at Post-Baseline – Value at Baseline
- Concomitant Medication is defined as any medication a subject has received concurrently with study treatment.
- Prior Medication is defined as any medication or therapies initiated prior to date of first dose of study drug. Medications that are started prior to the date of first dose of study drug and continue after the first dose of drug are considered to be both prior and concomitant medications.
- Treatment-Emergent Adverse Event (TEAE) – A TEAE is any adverse change from the subject's baseline condition that occurs on or after the date of the first dose of study drug through the duration of the clinical study.
- Related TEAE – Any TEAE with a reported relationship to study drug of 'possibly related'.
- Compliance = Calculated as the percentage of the number of vials used divided by the expected number of vials used, where the number of vials used is the number of used vials returned.

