9.2 Clinical Laboratory Evaluations

Descriptive summaries of actual (absolute) values and changes from baseline will be presented for Chemistry, Urinalysis, Complete Blood Count, PR, INR, and aPTT. These tables will be grouped by visit, and overall treatment.

The number and proportion of subjects with clinical laboratory values below, within, or above normal ranges, at each study visit will be tabulated (shift tables) for each clinical laboratory analyte by treatment group. Normal ranges will be provided by the central laboratory (URMC) used in this study.

Laboratory values will be displayed in data listings and those that are outside the normal range will be flagged, along with the corresponding normal ranges.

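### Laboratory extremes found off schedule are listed, but no summary or shift table in the SAP's readable text would show their size

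*SAP*

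**What the plan says.** Three SAP rules decide which laboratory results reach a table.

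- **Unscheduled draws** (SAP 6): "Assessments done on unscheduled visits will not be summarized but will be listed".
- **Repeats** (SAP 6.2): "repeat laboratory test results will not be used unless the original laboratory value is missing or indicated as invalid".
- **Premature withdrawal** (SAP 6.1): the PW result is assigned to the closest scheduled visit, earlier or later, and then "The data collected closest in time and date to protocol scheduled timing will be used for analysis".

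SAP 6.2 states the consequence: "Data not subject to analyses according to this plan will not appear in any tables or graphics"; such data go to listings only.

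SAP 9.2 plans descriptive summaries by visit, plus counts below, within and above the normal range, which "at each study visit will be tabulated (shift tables) for each clinical laboratory analyte by treatment group". In the listings, values are shown and "those that are outside the normal range will be flagged, along with the corresponding normal ranges". The readable text describes no worst-post-baseline table and no summary in multiples of a reference limit.

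Protocol 9.5.3.7 schedules laboratory draws at Baseline/Day 1 and Weeks 4, 13 and 26 (or PW), and asks for further samples when clinically indicated. Protocol 9.5.3.1.6 asks for immediate repeats of unexplained, clinically significant results, followed until they normalise.

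**The concern.** The protocol generates off-schedule results at the moments when a laboratory problem is suspected, and the SAP keeps those results out of the laboratory tables. Efficacy analysis has been removed (SAP 2.2, 8 and 10), so the study report is a safety report.

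The risks in question are reversible and can rise and resolve between draws. Protocol 7.3 describes a pilot subject whose transaminases rose and then normalised. The appended label (5.3) describes reversible neutropenia and thrombocytopenia that may be related to dose. Protocol 9.4.1.1 says of the dose after Week 13 that "it may be reduced on a case-by-case basis to manage subsequent drug-related AEs (e.g., elevated liver function tests"). Unless the Week 13 sample itself prompted it, the liver result behind such a reduction before Week 26 would come from an unscheduled draw and would appear in no laboratory summary. A reader of the tables could then see mild by-visit values and not learn how large the excursions were.

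**Working it through.** There is no planned figure to reproduce: the study is descriptive and its sample size has no statistical basis (SAP 5.1). The check has two parts.

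**1. What happens to each kind of result**

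| Result | Laboratory tables | Elsewhere |
|---|---|---|
| Scheduled, valid | Included; extremes show in the by-visit minimum and maximum | Listed |
| Unscheduled | Excluded (SAP 6) | Listed, flagged if out of range |
| Repeat of a valid original | Excluded (SAP 6.2); the original stays | Listed, flagged if out of range |
| PW, further from schedule than an existing value at the assigned visit | Excluded (SAP 6.1) | Listed, flagged if out of range |
| Any of these, if judged clinically significant by the investigator | As above | Also a TEAE, tabulated by preferred term, relationship and severity (Protocol 9.5.3.1.1; SAP 9.1) |

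The TEAE tables record that an event occurred. Protocol 9.5.3.1.3 grades severity mainly by symptoms and effect on function, not by laboratory multiples, so those tables do not give the peak or nadir.

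**2. How often a PW result would be displaced**

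Inputs:
- Scheduled laboratory days are 1, 29, 92 and 183 (Protocol 2.1), so the gaps are 29 − 1 = 28, 92 − 29 = 63 and 183 − 92 = 91 days.
- Possible PW days are Days 2 to 182 without Days 29 and 92: 181 − 2 = 179.
- Midpoints between visits are (1 + 29)/2 = 15, (29 + 92)/2 = 60.5 and (92 + 183)/2 = 137.5.

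A PW result is displaced when its nearest visit has already taken place with a value closer to the scheduled day.

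*Earlier draws exactly on schedule:*
- Days 30–60 go to Week 4: 31 days.
- Days 93–137 go to Week 13: 45 days.
- Sum: 31 + 45 = 76, and 76/179 = 42.5%.
- If Days 2–14 (13 days) may go to Baseline: 76 + 13 = 89, and 89/179 = 49.7%. Day 15 is then a tie.

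SAP 6.1 does not say whether Baseline is an eligible target. SAP 6.3 defines 302 Baseline as "The last non-missing measurement/assessment on the date of Week 26 Visit from HZNP-ACT-301", which favours the lower figure.

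*Week 4 and Week 13 draws both 3 days off target, the edge of the visit window:*
- Days 33–60 (28) and Days 96–137 (42): 28 + 42 = 70, and 70/179 = 39.1%.
- With Days 2–14: 70 + 13 = 83, and 83/179 = 46.4%.

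These are shares of calendar days, not of subjects; the documents give no withdrawal rate. They also give no number of unscheduled or repeat draws, so those two routes cannot be sized.

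**The case against.** The strongest objection is that the main example is already covered. A liver elevation that leads to a dose reduction is, in the protocol's terms, a drug-related adverse event. It would be counted in the TEAE tables, and its value would be listed and flagged. That is right, and it limits the consequence: the event is visible and only its size is missing from the tables. Abnormalities not judged clinically significant reach the listings alone.

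Other points narrow the concern further:

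- **Repeats.** The rule keeps the original, so it hides a peak only when the repeat is worse. The repeats the protocol requires follow results that already count as TEAEs. This stands.
- **The tables-and-graphics sentence.** By itself it excludes nothing; a planned worst-value table would make the data subject to analysis. This stands. The exclusion comes from the three specific rules.
- **The table list.** The planned-tables list (SAP 13) is unreadable in the public copy, and SAP 12 lets shells be updated separately, so a worst-value table may exist. This stands. Without an exception, however, the three rules would still keep these values out of it.
- **No broken promise.** The by-visit shift tables match Protocol 9.6.1, and the report is an abbreviated one. This stands.
- **Post-hoc tables are allowed.** They are, but they must be labelled post hoc, and the analytes and cut-offs would then be chosen with the data in view.
- **Baseline.** Subjects on active drug in HZNP-ACT-301 are already on treatment at 302 Baseline, so a shift from it can understate drug-related change. This stands; a summary against reference limits does not depend on baseline.

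**Conclusion.** The concern holds, as an optional improvement. The SAP's explicit rules keep unscheduled results, repeats of a valid original and some PW results out of the laboratory summaries and shift tables. Nothing in the readable text reports off-schedule ALT/AST peaks or blood-count nadirs in aggregate. No data are lost and no protocol commitment is broken.

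Only the PW route can be sized: 42% to 50% of possible withdrawal days with earlier draws on schedule, or 39% to 46% with the Week 4 and Week 13 draws at the window edge. The lower end of each range assumes that PW results are not assigned to Baseline. The conclusion also assumes that the chemistry panel and blood count include ALT, AST, neutrophils and platelets, which the readable text does not itemise.

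**What to change.** Keep the by-visit tables and the repeat rule as they are. Add one exception to SAP 6, 6.1 and 6.2:

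> Worst-post-baseline laboratory tables use all valid results (scheduled, unscheduled, repeat and PW) after the first open-label dose through the Follow-Up Safety Visit, or the last study contact if that visit is missed.

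This period follows the TEAE reporting period in Protocol 9.5.3.1.2. In SAP 9.2 add, for ALT, AST, neutrophils and platelets:

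1. A shift table from 302 Baseline to the worst post-baseline value, in the existing below/within/above categories.
2. The n, mean, SD, median, minimum and maximum of each subject's worst value as a multiple of the reference limit: highest ALT and AST over the upper limit, lowest neutrophils and platelets over the lower limit.

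Fix the cut-offs for any threshold counts before the data are reviewed. If the planned-tables list already contains these tables, only the exception sentence is needed.

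The cost is one sentence, one shift table and one summary, all from data already collected and listed. The drawback is that worst values depend on how often a subject was sampled and include isolated spikes. A footnote should say that subjects with more draws have more chances to show an extreme.

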- Low-contrast Sloan letter chart (LCSLC) Vision Test at Baseline/Day 1 (Week 26 of Study HZNP-ACT-301) and post-dose at Week 26 (or PW).
- For all subjects with a normal audiogram result at Screening in Study HZNP-ACT-301, Listening in Spatialized Noise-Sentences Auditory Test (LiSN-S) at Baseline/Day 1 (Week 26 of Study HZNP-ACT-301) and post-dose at Week 26 (or PW).
- Frataxin protein levels in whole blood, muscle biopsies (optional), and buccal cells at Baseline/Day 1 (Week 26 of Study HZNP-ACT-301) and post-dose at Weeks 13 and 26 (or PW).
- Functional staging of ataxia at Baseline/Day 1 (Week 26 of study HZNP-ACT-301), and post-dose at Weeks 13 and 26 (or PW).
- Physician Global Assessment and Patient Global Assessment at Baseline/Day 1 (Week 26 of Study HZNP-ACT-301) and post-dose at Weeks 13 and 26 (or PW).

Quality of Life Assessments

- Quality of life assessments (Modified Fatigue Impact Score [MFIS], and Pediatric Quality of Life [PedsQL] questionnaire or 36-item short-form health survey [SF-36]) at Baseline/Day 1 (Week 26 of Study HZNP-ACT-301) and Weeks 13 and 26 (or PW). The MFIS will be completed for all subjects. Subjects who completed the PedsQL during Study HZNP-ACT-301 will continue to complete the PedsQL in this study. Subjects who completed the SF-36 during Study HZNP-ACT-301 will continue to complete the SF-36 in this study.

Statistical Analyses:

All summaries will be presented by both the treatment received in HZNP-ACT-301 as well as overall.

Safety Endpoints

Adverse event and concomitant medication data will be summarized. Clinical laboratory safety data, vital sign data, echocardiogram data, and ECG interval data will be summarized with descriptive statistics for Baseline, post-dose, and change from Baseline to post-dose values. Shift tables will be presented for clinical laboratory values and ECG categorical results from Baseline to each post-dose visit. Physical examination findings will be listed by subject. Results of immunogenicity testing will be presented in tabular format.

Efficacy Endpoints

The primary efficacy endpoint is the observed change from Baseline to Week 26 for all subjects and from Baseline of HZNP-ACT-301 to Week 26 of HZNP-ACT-302 (52-week treatment duration) for subjects receiving active treatment in both studies in the FARS-mNeuro score. Results will be summarized descriptively.

Secondary Efficacy Endpoints

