While the approved ACTIMMUNE dose regimen does not involve initial dose escalation or titration, a recently completed study in healthy volunteers demonstrated a potential reduction in the severity of acute FLS when dose escalation to the standard dose was utilized [[Devane et al, 2014](#)]. This mirrors the clinical experience with other IFNs, particularly the interferon-betas (IFN- β s) used by multiple sclerosis patients where initial dose escalation using an acute titration regimen has been adopted. Natural tolerance to FLS develops relatively quickly in the majority of patients receiving IFNs and the dose escalation/titration minimizes the initial poor tolerability and treatment dropouts. It is expected that the use of the acute dose escalation as proposed in this protocol will facilitate subject retention during the early phase in the trial, particularly with dose escalation to 100 µg/m².

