2.2.1 Safety Endpoints

Adverse event and concomitant medication data will be summarized. Clinical laboratory safety data, vital sign data, echocardiogram data, and ECG interval data will be summarized with descriptive statistics for Baseline of HZNP-ACT-302, post-dose, and change from Baseline of HZNP-ACT-302 to post-dose values. Shift tables will be presented for clinical laboratory values and ECG categorical results from Baseline of HZNP-ACT-302 to each post-dose visit. Physical examination findings will be listed by subject. Results of immunogenicity testing will be presented in tabular format.

[figure not shown]

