9.1 Adverse Events

Missing and partially missing AE start and/or stop dates will be imputed for the purpose of statistical analysis, according to the specifications described in Section 6.1.

A summary of overall TEAEs, TEAEs, SAEs, TEAEs leading to PW, TEAEs by relationship to study drug, and severity of TEAEs will be presented by overall treatment.

Summaries and incidence rates (frequencies and percentages) of individual TEAEs by MedDRA System Organ Class (SOC) and preferred term will be displayed by overall treatment received. Such summaries will be displayed for TEAEs, SAEs, TEAEs leading to early termination, TEAEs by relationship to study drug, and TEAEs by severity

Each subject will be counted only once within each preferred term. If a subject experiences more than one TEAE within a preferred term only the TEAE with the strongest relationship or the maximum intensity, as appropriate, will be included in the summaries of relationship and intensity. No inferential statistical tests will be performed.

In the AE data listings, all AEs will be displayed. AEs that are not treatment-emergent will be flagged.

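### The SAP groups every summary by an undefined overall treatment and omits, without declaring it, the split by HZNP-ACT-301 treatment that the protocol requires

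*SAP*

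**What the plan says.** The Statistical Analyses paragraph of the protocol synopsis sets the rule: "All summaries will be presented by both the treatment received in HZNP-ACT-301 as well as overall". It applies to all summaries, safety included.

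SAP Section 6 gives a different general rule: "Additionally, all summaries will be presented by overall treatment". The same term, or a variant, recurs in Sections 7.1, 7.3 and 9.1 to 9.6. In Section 9.1, for example, adverse event incidence by system organ class and preferred term "will be displayed by overall treatment received".

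The SAP also uses a second term, treatment group. Section 6 says percentage denominators are in general "based upon the total number of subjects in the study population for the treatment group", and Section 9.2 says laboratory results relative to the normal range "will be tabulated (shift tables) for each clinical laboratory analyte by treatment group". Neither term is defined in Section 6.3 or elsewhere in the readable SAP.

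SAP Sections 2.2 and 10 list the changes from the protocol. Both mention only the removal of efficacy.

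**The concern.** Long-term safety is the primary objective, and the Safety Population combines two exposure histories. Former placebo subjects meet the drug for the first time in this study. Former ACTIMMUNE subjects enter having completed 26 blinded weeks (Protocol 9.3.1), so they carry the 52-week evidence and are also selected for having stayed on treatment.

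The documents give three reasons why the groups may look different:

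- **Tolerance.** Protocol 7.3 states: "Natural tolerance to FLS develops relatively quickly in the majority of patients receiving IFNs".
- **Event counting.** Protocol 9.5.3.1.2 treats events still ongoing from HZNP-ACT-301 as baseline signs or symptoms. A drug reaction that persists unchanged in a former ACTIMMUNE subject is therefore not treatment-emergent here. The same reaction starting in a former placebo subject is.
- **Baseline.** SAP 6.3 defines "302 Baseline = The last non-missing measurement/assessment on the date of Week 26 Visit from HZNP-ACT-301". SAP 2.2.1 summarises "change from Baseline of HZNP-ACT-302 to post-dose values" for laboratory, vital sign, echocardiogram and ECG data. For former placebo subjects this is an off-drug to on-drug contrast; for former ACTIMMUNE subjects it is on-drug to on-drug.

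A pooled column is a valid description of the mixed population, and the protocol asks for it as well. On its own it cannot show how either group fared.

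**Working it through.** The plan states no sample size, arm split or event rate for this study, so there is no figure of its own to reproduce. The check is first textual, then a bound under stated assumptions.

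**Text, side by side**

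| Question | Protocol | SAP (readable text) |
|---|---|---|
| Grouping of summaries | 301 treatment, and overall (synopsis) | *Overall treatment* (6, 7.1, 7.3, 9.1–9.6); *overall treatment received* (9.1, 9.2.1) |
| Denominators and laboratory shift tables | Not specified separately | *Treatment group* (6, 9.2) |
| Definition of those terms | Groups named directly | None, including in 6.3 |
| Treatments given in 302 | ACTIMMUNE for all (9.4.8) | ACTIMMUNE for all (3) |
| 301 treatment as a grouping | Required | Not used. It appears in the design text and schedule footnotes (3) and in the efficacy objectives (2.1), whose analyses are removed (8) |
| Declared change in grouping | – | None (2.2 and 10 cover efficacy only) |

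Since 302 has one treatment, only the 301 arm can separate subjects into treatment groups. A rule that does not name that arm leads, read literally, to one column.

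**How far a pooled figure can sit from the first-exposure figure**

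All inputs here are assumptions:

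- p = share of the Safety Population with prior ACTIMMUNE: 1/3, 1/2 or 2/3.
- d = first-exposure event rate minus continued-exposure event rate, in percentage points: 0, 5, 10 or 20.
- c = mean change from 302 Baseline in continued-exposure subjects, as a fraction of that in first-exposure subjects: 0, 0.5 or 1.

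*Event rates.* Pooled rate = (1 − p) × r + p × (r − d) = r − p × d, where r is the first-exposure rate. The gap is p × d:

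| d (points) | p = 1/3 | p = 1/2 | p = 2/3 |
|---|---|---|---|
| 0 | 0 | 0 | 0 |
| 5 | 1.7 | 2.5 | 3.3 |
| 10 | 3.3 | 5.0 | 6.7 |
| 20 | 6.7 | 10.0 | 13.3 |

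*Change from 302 Baseline.* Pooled mean change ÷ first-exposure mean change = (1 − p) + p × c:

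| c | p = 1/3 | p = 1/2 | p = 2/3 |
|---|---|---|---|
| 0 | 67% | 50% | 33% |
| 0.5 | 83% | 75% | 67% |
| 1 | 100% | 100% | 100% |

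For example, at p = 1/2 and c = 0 the ratio is 0.5 + 0.5 × 0 = 0.5: the pooled mean shows half of the change seen on first exposure.

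**The case against.** The strongest reply is that the SAP is loosely worded and the split was never dropped. *Overall treatment received* shares its key words with the protocol's rule, and *treatment group* makes little sense in a single-treatment study unless it means the 301 arm. SAP Section 12 also allows counts per classification factor in column headers. The table shells, where columns would be shown, are not readable. This reading is possible, so the finding is limited to the SAP prose. It does not remove the problem: a programmer cannot tell from the text whether to build one column or three, or which denominator to use. Section 12 also lets the shells change independently of the SAP, so they cannot stand in for the missing rule.

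Other points on that side:

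- **Promise to follow the protocol.** SAP Sections 4.2 and 6 commit to the analyses identified in the protocol and the SAP. Those sentences mainly fix timing and do not override a specific, conflicting grouping rule.
- **Synopsis only.** Protocol 9.6 does not repeat the rule. That is true, but nothing there contradicts it.
- **Re-titration.** Everyone restarts at the lowest dose, and the sentence in Protocol 7.3 that mentions tolerance goes on to say titration limits early poor tolerability. This may narrow the difference between groups. It stands, and it is why the ranges above include no difference.
- **Entry exceptions.** Protocol 9.7 lets the Medical Monitor consider exceptions to entry criteria, so completion of 26 weeks may not be universal. This is trivial here.
- **Limited harm.** The report is an abbreviated, descriptive safety report, all data are listed, and subjects keep their 301 identifier, so a split can be produced later. This limits the damage, but a later unplanned split is weaker than the pre-specified one the protocol already promises.

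**Conclusion.** The concern holds. The protocol requires two presentations. The readable SAP states one, in a term it does not define, and declares no change. Confidence is high for this mismatch in the text; whether the shells already carry the 301 columns cannot be checked.

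The numerical consequence is unknown. Under the assumed shares, a pooled event rate would miss the first-exposure rate by 0 to 13.3 points as the true difference runs from 0 to 20 points. A pooled mean change would show between 33% and 100% of the first-exposure change. These figures illustrate the mechanism and do not estimate what this trial would show.

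The point should be fixed because it bears on the primary objective and the correction is cheap. It does not invalidate the overall column.

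**What to change.** In SAP Section 6, state that every summary is shown in three columns (301 placebo, 301 ACTIMMUNE, and overall), with each column's own Safety Population count as the general denominator. Replace *overall treatment*, *overall treatment received* and *treatment group* with matching wording in Sections 6, 7.1, 7.3 and 9.1 to 9.6, and bring the table shells into line where they differ. If a single pooled column is intended, define the term, and record and justify the departure from the protocol in Section 10.

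The cost is SAP wording plus extra columns in any shell that lacks them. No new data are collected, and the protocol's own plan already needs the 301 treatment code. The drawback is a smaller count per column, which is minor because the summaries are descriptive and SAP 5.1 says no inference will be drawn.
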